11.4. Reporting of Adverse Events

Participants will be asked to contact the study site immediately in the event of any significant adverse event. The Chief Investigator shall be informed immediately of any reportable serious adverse events and shall determine seriousness and causality in conjunction with any treating medical practitioners.

In the event of a pregnancy occurring in a trial participant or the partner of a trial participant monitoring shall occur during the pregnancy and after delivery to ascertain any trial related adverse events in the mother or the offspring. Where it is the partner of a trial participant consent will be obtained for this observation from both the partner and her medical practitioner.

All reported serious adverse events will be recorded and reported to the MHRA and REC as part of the regular mandatory reports. SUSARs will be reported within the statutory

timeframes to the MHRA and REC as stated below. The Chief Investigator shall be responsible for all adverse event reporting.

11.5. Participant Removal from the Study due to Adverse Events

Any participant who experiences an adverse event may be withdrawn from treatment at the discretion of the Investigator.

12. Duration of Study and Participant Involvement

12.1. Duration of Participant Involvement in the Study

Treatment (including surgery) will last for a minimum of 22 and a maximum of 24 weeks weeks. The patient will then have a final post surgery follow-up at 12 weeks, making the total maximum duration 36 weeks.

12.2. Duration of the Study

This trial is estimated to last a total of 68 weeks, from initiation of the (first) study site to completion of the last patient.

12.3. End of Study

The end of the trial will be defined as the last patient last visit.

13. Laboratory sub-study: Autologous self-vaccination against melanoma antigens

Peripheral blood lymphocytes will be isolated and cryopreserved. HLA typing will be done. Both pre and post treatment samples from each patient will be analysed in the same ELIspot assay. The frequency of lymphocytes releasing interferon γ in response to stimulation with peptide epitopes derived from melanocyte differentiation and cancer-testis antigens will be measured using a validated assay.

13.1. Blood sample processing at the investigator site

The investigator site should inform the WTCRF that a sample is to be taken, giving 48 hours notice preferably. Samples should not be sent on a Friday if possible.

Pre-addressed secure packaging and sodium heparin vacutainer bottles will be provided by the study centre.

Samples will be labeled with the date and patient study number and placed within the secure packaging. A trial specific form recording the study participant number, date, evidence of patient consent, time and date the samples were taken, and any untoward events in sample handling will be completed and sent.

Extremes of temperature should be avoided. Blood samples should be maintained between 10-20°C.

Samples will be dispatched by same day courier to:

[name] Wellcome Trust Clinical Research Facility University Hospitals Birmingham NHS Foundation Trust Queen Elizabeth Hospital [name] [contact]

13.2. Sample storage and custodian

At the Wellcome Trust Clinical Research Facility in Birmingham the samples will be stored at -150°C in liquid nitrogen in swipe access controlled area and therefore only authorised personnel have access. The samples will be kept in a dedicated tank.

[name] is the custodian of the samples. Analysis will be conducted by a research assistant, overseen by [name] and [name] (Director of the Human Biomaterials Resource Unit).

If any samples remain at the end of this study they will either (i) be stored by the research group pending further ethical approval, or (ii) be transferred to the University of Birmingham HTA-licensed tissue bank. It will be made clear in the information sheet and the consent form that samples may be stored for use in future ethically approved research.

14. Details of Investigational Medicinal Products

14.1. Description

This study will investigate the effectiveness of imiquimod as a treatment for lentigo maligna. Participants will apply imiquimod 5% cream (Aldara[®]) supplied by MEDA Pharmaceuticals Ltd. (UK). Each sachet contains 12.5 mg of imiquimod in 250 mg cream (5%). The appearance is white to slightly yellow cream. The CAS number for imiquimod is 99011-02-6.

The excipients are:

- isostearic acid
- benzyl alcohol
- cetyl alcohol
- stearyl alcohol
- white soft paraffin
- polysorbate 60
- sorbitan stearate
- glycerol
- methyl hydroxybenzoate (E218)
- propyl hydroxybenzoate (E216)

- xanthan gum
- purified water

Details of the chemical and pharmacological properties of imiquimod can be found in the current Summary of Product Characteristics document (SmPC).

14.2. Packaging and Labelling

As there is no blinding in this study, the imiquimod will be prescribed in its standard packaging, with additional labelling to comply with regulatory requirements. MEDA will ship the imiquimod to a central pharmacy at the Clinical Trial Pharmacy Department, University Hospitals Nottingham, Queens Medical Centre Campus, Nottingham. The central pharmacy will then dispatch study drug to the local site pharmacies where the final labelling will be put on prior to dispensing.

Imiquimod is prescribed in sachets. Participants will be advised that sachets should not be re-used once opened.

14.3. Storage, dispensing and Return

The study supplies will be kept separately to other pharmacy supplies and labelled accordingly. Storage will be at not more than 25°C. After dispensing, participants will be instructed to store the sachets at not more than 25°C. Unused supplies will be returned to local pharmacy for destruction.

The clinical trials pharmacist or designee at the hospital will dispense the medication and keep detailed dispensing records.

14.4. Known Side Effects of imiquimod

These are detailed in the Summary of Product Characteristics (SmPC).

15. Outcome Measures

15.1. Primary Outcome Measure

• Pathological complete regression (PCR) in the mapped biopsied and resected LM using 2 mm slices.

15.2. Secondary Outcome Measures

- Clinical assessment of response after imiquimod treatment:
 - Assessment of clinical response based on examination and presurgical biopsies
 - Pathological assessment of residual LM outside the clinically mapped margins of disease
 - Accuracy of map 1 and map 2 and 5mm surgical margin in predicting complete excision of lentigo maligna

The pathological response in the entire resected lesion will be compared with that predicted from clinical examination and biopsies taken before surgery, post imiquimod treatment. We will assess whether adequate surgical margins can be determined using clinical maps. It is essential to know the accuracy of the method of clinical assessment of response.

- Clinical feasibility of imiquimod treatment:
 - Number of reported local adverse reactions and systemic adverse reactions. These will be collected from the patient held diary and assessment by the investigator
 - o Adherence to treatment schedule
 - Acceptability of imiquimod treatment. This will be collected by a visual analogue scale completed weekly by the participant.
 - o Number and reasons for withdrawal from imiquimod treatment
- Number of consultations with NHS staff during imiquimod treatment
- Frequency of functional T cell responses recognising peptide epitopes in melanocyte differentiation and cancer-testis antigens.

Circulating immune responses to proteins expressed within melanoma will be measured using blood draws taken before imiquimod treatment and after completion of imiquimod therapy but before surgery. The demonstration of a circulating immune response would be an important finding that would strongly support the investigation of imiquimod as primary therapy for melanoma, even if coupled with subsequent surgery because of the potential for such an immune response to be preventative against recurrence or invasive disease.

 Measurement of hypothetical treatment preferences for surgery or imiquimod for LM using standard gamble technique.

The clinical significance of the findings of this trial were pre-determined by consultation with UK dermatologists. This small scale trial will be used to enable patients to actively contribute to the interpretation of results and design of clinical guidelines or a randomised controlled trial.

15.3. Stopping Guideline and Discontinuation

The following will result in the trial being terminated:

- Unexpected toxicity or other major safety concerns. The DMC will be pivotal in making recommendations around safety.
- Insurmountable issues with trial conduct (e.g. poor recruitment, loss of resources).
- A regulatory decision, a change in opinion of the Research Ethics Committee (REC) or sponsor withdrawal.

Recruitment at a particular study site may be stopped for reasons of low recruitment or compliance issues.

The Sponsor reserves the right to discontinue this trial at any time for failure to meet expected enrolment goals, for safety or any other administrative reasons. The Sponsor shall take advice from the Trial Steering Committee and Data Monitoring Committee as appropriate in making this decision.

16. STATISTICS

16.1. Sample size

This trial enables the discrimination of a pathological CR rate of 60% from 85%. These limits were established using the responses of 174 UK dermatologists to a questionnaire about how the results of treating LM would impact on their practice. A CR rate >85% would be persuasive evidence for imiquimod as primary treatment for LM for 75% dermatologists; a CR rate <60% would be persuasive against the use of imiquimod.

Using A'hern's method (20) and with 95% power, the probability of a false positive is 5%. The probability of a false negative is also 5%. The study requires 33 patients and an observed CR rate of 25/33 (76%) or above would be sufficient to support proceeding to a RCT. To account for attrition, the target will be 40 patients.

There is a decision rule regarding whether to proceed to a randomised controlled trial or not based on the primary outcome measure (observed pathological complete regression (CR) rate), exceeding 25/33 evaluable patients (20). The secondary outcome measurements are very important and might contribute to decision making, particularly if the primary outcome falls in between the 60% and 85% limits. Highly positive secondary outcomes might support some kind of further research despite failing to meet the primary objective. Alternatively, highly adverse secondary outcomes might dissuade from a RCT despite achieving the primary objective. However, overall their role will remain secondary. The secondary objectives will also guide the design of a subsequent RCT.

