10.7. Withdrawing from the study / stopping medication early

The participant will stop imiquimod treatment early for the following reasons:

- Intolerable local or systemic toxicity from imiquimod
- Progression of lentigo maligna suggesting the development of invasive disease. These participants will progress immediately to surgery.
- Any participant who becomes pregnant during the study.
- Withdrawal of consent.

Patients who withdraw from imiquimod treatment will still require surgical treatment. If the patient agrees, they will be treated by mapping and surgical excision at least **12 weeks** after the **first** application of imiquimod and a minimum of **10 weeks** after the **last** application of imiquimod (once the inflammation has subsided). These data will be included in the outcome analysis and these patients will not be replaced. By continuing to surgery, at least the primary outcome data will be collected.

Patients who refuse surgery will be included in the total dataset but will be replaced as it will not be possible to obtain primary outcome data for these patients. All attempts will be made to encourage participants to remain in the study.

Participants who withdraw consent will be withdrawn from the trial. The participants will be made aware that this will not affect their standard of care. Participants will be made aware (via the information sheet and consent form) that should they withdraw the data collected will be retained and used as part of the study analysis.

Participants will not be accepted as lost to follow-up unless phone calls, letters or visits to the participant or GP have been fruitless.

11. Adverse Events

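### The single cut-off of 25/33 is right for 33 evaluable patients, but 40 are enrolled; read as a rate it loses power at 36, 37, 39 and 40, where a compliant cut-off exists

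*Protocol*

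**What the plan says.** Section 16.1 of the protocol sets the design with A'Hern's exact single-stage method: 60% against 85%, with false-positive and false-negative probabilities of 5% each. The rule reads: "The study requires 33 patients and an observed CR rate of 25/33 (76%) or above would be sufficient to support proceeding to a RCT". The same section adds: "To account for attrition, the target will be 40 patients". A later paragraph there restates the rule in terms of evaluable patients, again with 25/33. No cut-off is given for any other number, and nothing says which 33 patients would decide if more were available.

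Three other places bear on how many patients will have a result:

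- Section 4.1 caps enrolment at forty.
- Section 10.7 says of patients who stop imiquimod early and go on to surgery: "These data will be included in the outcome analysis and these patients will not be replaced". Patients who refuse surgery are replaced.
- Section 16.2 makes the primary analysis intent-to-treat and includes early stoppers who reach surgery.

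**The concern.** An exact single-stage rule holds its error rates only for the number of patients it was computed for. With 40 enrolled, exactly 33 evaluable patients requires exactly 7 of 40 (17.5%) to have no result. The protocol states no attrition rate, and its rules on early stoppers and refusers work to keep the number up.

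If the number is not 33, the only instruction available is the printed rate. Because counts are whole numbers, carrying 25/33 to another denominator can demand one responder more than the stated error limits require. The decision at stake is the study's stated purpose in section 7.1: whether to proceed to a randomised trial. In an open-label, single-arm study, a cut-off still to be settled when results are visible is open to dispute.

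**Working it through.** **Inputs.** p0 = 0.60, p1 = 0.85, limits of 5% and 5%, n = 33 and r = 25, all from section 16.1. Enrolment of 40 is from sections 4.1 and 16.1. Assumption: the denominator is the number of patients with a pathological result.

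**Formulas.** For n evaluable patients and a go at r or more responders:

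- alpha = P(X ≥ r), X ~ Bin(n, 0.60)
- power = P(X ≥ r), X ~ Bin(n, 0.85)

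**Step 1: the plan's own figure.** With n = 33 and r = 25, alpha = 4.44% and power = 95.05%. A search over n from 10 upwards finds 33 to be the smallest n that meets both limits. The stated design is reproduced.

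**Step 2: the threshold as a rate.** The cut-off is the smallest whole number not below 25n/33. For n = 40, 25 × 40/33 = 30.30, so r = 31. For n = 37, 25 × 37/33 = 28.03, so r = 29.

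**Step 3: the exact cut-off.** For each n, take the smallest r with alpha at or below 5%.

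| n | Rate rule r | alpha | power | Exact r | alpha | power |
|---|---|---|---|---|---|---|
| 33 | 25 | 4.4% | 95.05% | 25 | 4.4% | 95.05% |
| 34 | 26 | 3.4% | 94.1% | 26 | 3.4% | 94.1% |
| 35 | 27 | 2.6% | 93.1% | 27 | 2.6% | 93.1% |
| 36 | 28 | 2.0% | 92.0% | 27 | 4.5% | 96.5% |
| 37 | 29 | 1.5% | 90.8% | 28 | 3.5% | 95.8% |
| 38 | 29 | 2.7% | 95.1% | 29 | 2.7% | 95.1% |
| 39 | 30 | 2.0% | 94.2% | 29 | 4.5% | 97.5% |
| 40 | 31 | 1.6% | 93.3% | 30 | 3.5% | 97.0% |

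At 36, 37, 39 and 40 the rate rule asks for one responder more than the exact rule. Its false-negative rate there is 8.0%, 9.2%, 5.8% and 6.7% (100% minus power), against a stated 5%. At n = 40 the disputed result is 30/40 = 75.0%, which is below 25/33 = 75.76%.

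Reading the threshold as a literal 76%, or as strictly above 25/33, gives the same cut-offs for n = 34 to 40. Those variants matter at n = 33 itself, where they would require 26/33 (alpha 1.9%, power 88.9%).

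**Step 4: below 33.** The exact cut-offs are 23/30 (alpha 4.4%, power 93.0%), 24/31 (3.3%, 91.8%) and 25/32 (2.5%, 90.4%); the rate rule gives the same three. At n = 29 the rate rule gives 22/29, with alpha 5.7% and power 94.1%; the exact rule needs 23/29 (2.3%, 86.7%).

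**Step 5: what no cut-off can repair.** At n = 34, n = 35 and every n from 10 to 32, no r meets both limits. At n = 34, for example, 26 gives power 94.1%, while 25 gives alpha 7.3%. The shortfall at these n comes from the number of patients, not from carrying 25/33 over.

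**The case against.** The strongest reply is that the rate reading is nearly harmless. It is the natural reading, since section 16.1 words the threshold as an observed rate with a percentage. Under it, alpha stays at or below 3.4% from 34 to 40, so a false go is never more likely than stated. Both limits hold at 38, and power is within 2 points of 95% at 34, 35, 39 and 40. Section 16.1 also lets secondary outcomes weigh in when the result lies between 60% and 85%, as 30/40 does, and section 16.2 plans no formal testing. All of that stands and limits the size of the point. It does not remove it: section 16.1 still claims a 5% false-negative probability for a decision rule, and at four attainable numbers the rule as written misses it when a compliant cut-off is available.

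A second reply is that a cut-off for the attained number belongs in the statistical analysis plan, which is not at hand. That would be fair if the protocol were silent. Here the protocol itself prints the rule, the error rates and the enrolment of 40, and these do not fit together except at 33 or 38.

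A reader might go further and take 25 as a fixed count of responders whatever the denominator. That would give alpha of 16.2% at n = 36 and 44.0% at n = 40. The text does not support it: 25/40 is 62.5%, which cannot satisfy a threshold printed as 76%. Those figures are a reason to rule the reading out in words, not a measure of the defect.

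The breach of alpha at n = 29 likewise needs 11 of 40 patients (27.5%) without a result, well beyond the 17.5% implied by 33/40.

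**Conclusion.** The stated design is correct at n = 33, and there is no arithmetic error in it. The defect is that the protocol gives one cut-off for one denominator while its own rules make other denominators likely. Applied as a rate, the rule is conservative for 34 to 40 patients. It falls short of 95% power by 3.0 points at n = 36, 4.2 at 37, 0.8 at 39 and 1.7 at 40, each avoidable by lowering the cut-off by one. The shortfalls at 34, 35 and below 33 are unavoidable at those numbers and should simply be acknowledged.

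This rests on the denominator being patients with a pathological result, and on true rates of exactly 60% and 85% for the error calculations. Severity is moderate: a real misfit in the primary decision rule, small in size and easy to repair.

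**What to change.** State in section 16.1, before results are known, that the decision uses all evaluable patients and that a go requires at least r responders, where r is the smallest count with P(X ≥ r | 60%) at or below 5%. Print the cut-offs with exact alpha and power for each: 23/30, 24/31, 25/32, 25/33, 26/34, 27/35, 27/36, 28/37, 29/38, 29/39, 30/40, extended downwards if wished.

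Add one sentence saying that 25 is not a fixed count. Use one phrase throughout (at or above the cut-off), since the section now also speaks of exceeding 25/33. Say too how replacement of surgery refusers fits with the cap of forty, because that sets the range the table must cover.

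The cost is one small table and a few sentences, with no more patients and no change of design. The price is admitting that power is slightly below 95% at 34 and 35 (94.1% and 93.1%), and lower at some numbers below 33 (for example 90.4% at 32).

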4. STUDY DESIGN

4.1. Overview

This is a multicentre, open label, non-randomised, single-stage trial to discriminate between a pathological CR rate of <60% and >85%. It is anticipated that approximately fourteen recruiting centres will take part.

[figure not shown]
A maximum of forty patients with lentigo maligna (LM) will undergo clinical lesion mapping (map 1) followed by 12 weeks topical imiquimod treatment. The dose of imiquimod will be adjusted according to local toxicity. Scheduled study visits during treatment will be at 1, 2, 4, 8 and 12 weeks. At these visits, tolerability and adverse reactions will be recorded with the aid of patient diaries. Any unscheduled consultations for dose adjustments will be recorded. After treatment, clinical response will be determined and the LM will be remapped if there is contiguous pigmentation outside the previously mapped area (map 2). This visit will be at 10 to 12 weeks after the last application of imiquimod. All patients will progress to biopsy, then surgical excision. This will include map 1 in all patients, and map 1 plus map 2 in those with pigmentation outside map 1, plus a margin of apparently healthy tissue. The entire specimen will be sectioned and examined histologically to determine pathological clearance and the presence of LM outside the mapped area. Patients who withdraw from imiquimod treatment prior to 12 weeks will still require surgical excision. This will be done at least 12 weeks after the first application of imiquimod and 10 to 12 weeks after the last application of imiquimod and 10 to 12 weeks after the last application of imiquimod and 10

The immune response against melanocyte differentiation antigens will be measured by ELIspot assays using blood samples drawn at baseline and the week 12 visit.

An overview of the study design is shown in figure 1.

Figure 1

Flow diagram showing progression of participants through the study.

Schedule of Assessments Table

Week	Pre- study	Baseline -1	0	1	2	4	8	12	22-24 (Post TX)		1-2 wks post SX	12 wks post SX
Biopsy	Х								X			
Informed consent		Х										
Pregnancy test		Х										
Medical history		Х										
Demographic data		Х										
Mapping of lesion		Х							Х	S		
Photograph lesion		Х							Х	C		
Blood samples for		X						x				
immune assay		^						^		ス		
Blood Sample for HLA		X								-		
typing		~								G		
User Opinion										_		Х
Questionnaire										Π		~
Study drug administered			Х	Х	Х	х	Х	Х		ת		

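### Section 16.1 gives the go/no-go threshold as both at least 25/33 and more than 25/33, and the second does not have the stated 95% power

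*Protocol*

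**What the plan says.** All the relevant text is in Protocol section 16.1.

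- **Limits.** "This trial enables the discrimination of a pathological CR rate of 60% from 85" per cent. The limits come from a survey of UK dermatologists. Section 4.1 repeats them and describes the design as an "open label, non-randomised, single-stage trial to discriminate between a pathological CR rate of <60% and >85" per cent.
- **Method and error rates.** "Using A'hern's method (20", reference 20), and "with 95% power, the probability of a false positive is 5" per cent. "The probability of a false negative is also 5" per cent.
- **Rule A**, in the same paragraph as the error rates and the requirement of 33 patients: "an observed CR rate of 25/33 (76%) or above would be sufficient to support proceeding to a RCT".
- **Rule B**, in the following paragraph, in the sentence introduced as the decision rule: the observed pathological CR rate "exceeding 25/33 evaluable patients (20", citing the same reference.

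Nothing elsewhere in the protocol says which rule governs.

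**The concern.** The outcome is a count, so the two wordings are different rules. Out of 33, Rule A is met by 25 or more complete regressions and Rule B by 26 or more. A result of exactly 25 means go under A and no-go under B.

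This threshold carries most of the trial's inferential weight. Section 7.1 gives the purpose of the study as deciding whether to move to a randomised trial, and section 16.2 rules out formal statistical testing. If 25 of 33 were observed, the choice between the wordings would be made with the data in view, which a prespecified rule is meant to prevent.

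The two rules also have different error rates, while section 16.1 states only one pair. At most one of the rules can be the design described there.

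**Working it through.** **Inputs, all from section 16.1.** n = 33 evaluable patients; p0 = 0.60; p1 = 0.85; false-positive risk at most 0.05; false-negative risk at most 0.05 (power at least 0.95); exact single-stage design.

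**Formula.** With X the number of pathological complete regressions, X ~ Binomial(n, p), and a rule of r or more:

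- false-positive risk = P(X ≥ r | n, p0)
- power = P(X ≥ r | n, p1)
- P(X ≥ r | n, p) = Σ from k = r to n of C(n, k) p^k (1 − p)^(n − k)

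**Step 1: reproduce the stated design.** The smallest n with a cut-off r giving false-positive risk ≤ 0.05 and power ≥ 0.95 is n = 33, with r = 25. This matches the protocol. The 76% in brackets also matches: 25/33 = 0.758.

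**Step 2: compare cut-offs at n = 33.**

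| Rule | False-positive risk (p = 0.60) | Power (p = 0.85) | False-negative risk | Meets 5% / 5%? |
|---|---|---|---|---|
| 24 or more | 9.23% | 98.05% | 1.95% | No |
| 25 or more (Rule A) | 4.44% | 95.05% | 4.95% | Yes |
| 26 or more (Rule B) | 1.86% | 88.93% | 11.07% | No |
| 27 or more | 0.66% | 78.26% | 21.74% | No |

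Only 25 or more satisfies both limits. It clears the power target by just 0.05 percentage points, so moving the threshold by one patient breaks the stated design.

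**Step 3: the gap between the rules.** They differ only at X = 25, so the power lost is the probability of that single outcome:

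- at p = 0.85: 0.9505 − 0.8893 = 0.0612. Direct check: C(33, 25) × 0.85^25 × 0.15^8 = 13,884,156 × 0.85^25 × 0.15^8 = 0.0612.
- at p = 0.60: 0.0444 − 0.0186 = 0.0259 from the unrounded values.

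The false-negative risk therefore rises from 4.95% to 11.07%, a factor of 2.2.

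**Step 4: how likely is the disputed result?** P(X = 25 | n = 33) is 6.1% at a true rate of 85%, 13.4% at 80% and 15.9% at 75%. It is most likely when the true rate lies between the two design limits.

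**The case against.** The best counter-argument is that this is a slip in one word and not an underpowered design. The error rates, the 33 patients and Rule A stand together in one paragraph. Rule B cites the same reference and claims no error rates of its own, so a careful reader can infer that 25 or more was meant. That is fair, and it is why the fix is small. It does not remove the contradiction, because the loose word sits in the sentence labelled as the decision rule.

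Three further points have some force:

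- **The conflict is narrow.** Read as rates, the two wordings can differ only where the observed rate equals 25/33 exactly. Since 25 and 33 share no common factor, this requires exactly 33 evaluable patients for any number up to the target of 40. At 40 evaluable, for example, 40 × 25/33 = 30.3, so both wordings require 31. This stands as a limit on the finding. However, 33 is the number for which the rule is written and the error rates are quoted.
- **The stricter reading is cautious.** Rule B lowers the false-positive risk to 1.9%. True, but the protocol also promises a 5% false-negative risk, and Rule B does not keep it.
- **The rule is not mechanical.** Section 16.1 lets secondary outcomes inform the decision, especially between 60% and 85%, and 76% lies in that range. The same paragraph keeps them secondary, though, and separates achieving the primary objective from failing it. That distinction needs a single threshold.

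**Conclusion.** The concern holds. Section 16.1 contains two incompatible thresholds, and only at least 25 of 33 agrees with the stated 5% false-positive and 5% false-negative risks. Taken literally, the sentence called the decision rule has 88.9% power, about 6 percentage points below the stated 95%.

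This rests on exactly 33 evaluable patients, the 60% and 85% limits and independent binomial outcomes, as in the design the protocol cites. The sample size calculation is correct. The conflict alters the decision only at exactly 25 of 33. It does not affect the estimated response rate, its confidence interval or any patient procedure. It still needs correcting, because it lies in the primary decision criterion and can reverse the trial's conclusion.

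**What to change.** In the third paragraph of section 16.1, replace the strict inequality so that the rule to proceed reads: *at least 25 pathological complete regressions among 33 evaluable patients*. State the exact operating characteristics beside it: false-positive risk 4.4% at a true rate of 60% and power 95.05% at a true rate of 85%. The 5% and 5% figures are design limits that this rule already meets, so the exact values are not a correction. They do make plain which count the error rates belong to.

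The cost is one sentence in the protocol, with no change to sample size, recruitment or conduct. It should be made before the primary outcome data are seen.
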